3.4. Duration of Treatment

[figure not shown]
The duration of the Sentinel Cohort 1 in Part 1 of the study is 10 days. Subjects who successfully complete the functional monotherapy, defined as a $> 0.5 \log_{10}$ reduction in plasma HIV-1 RNA from baseline, will be administered GS-9131 (60 mg) + BIC (30mg)+ DRV (800 mg) +RTV (100mg) through Week 24. **CCI**

The duration of Sentinel Cohort 2 and Randomized Cohorts in Part 1 of the study is 15 days each. Subjects who successfully complete the 14 day functional monotherapy, defined as a $> 0.5 \log_{10}$ reduction in plasma HIV-1 RNA from baseline or who are from the PTM arm, will be administered GS-9131 + BIC (75 mg) + TAF (25 mg) through Week 24. Doses of GS-9131 for subjects in the Sentinel Cohort 2 and Placebo cohort will be 180 mg; doses of GS-9131 and PTM for subjects in the Randomized Cohorts Treatment Arms A-C will correspond to the respective dose selected for cohorts (A-C). All subjects will continue a regimen of GS-9131 + BIC (75 mg) + TAF (25 mg) at the assigned GS-9131 dose until determination of the optimal GS-9131 dose following Part 1 data review of the Randomized Cohort. **CCI**

[figure not shown]
Figure 2. Study Schema – Cohort 1

- a Randomization and dosing into the Randomized Cohort of Part 1 will begin after the Day 10 safety and efficacy data from the 10 subjects in the Sentinel Cohort are reviewed.
- b Subjects on GS-9131 (including all subjects in the Sentinel Cohort and those on Treatment Arm A, B, and C of the Randomized Cohort) who have a $\leq 0.5 \log_{10}$ decline in HIV-1 RNA will be discontinued from the study and will not be eligible to continue into Part 2 of the study. The Sponsor will notify the site regarding subject enrollment criteria for Part 2 prior to the visit.”
- c Subjects who complete Day 10 of Part 1 (from either the Sentinel Cohort or Treatment Arm D of the Randomized Cohort) will discontinue their GS-9131 or PTM but remain on their failing ARV regimen until the site is notified of the subject’s eligibility to proceed to Part 2.

Figure 3. Study Schema – Cohort 2

- a. Randomization and dosing into the Randomized Cohort of Part 1 will begin after the Day 15 safety and efficacy data from the Sentinel Cohort is reviewed.
- b. Subjects on GS-9131 (including all subjects in the Sentinel Cohort and those on Treatment Arm A, B, and C of the Randomized Cohort) who have a ≤ 0.5 log₁₀ decline in HIV-1 RNA will be discontinued from the study and will not be eligible to continue into Part 2 of the study. The Sponsor will notify the site regarding subject enrollment criteria for Part 2 prior to the visit.
- c. Subjects who complete Day 14 of Part 1 (from either the Sentinel Cohort or Treatment Arm D of the Randomized Cohort) will discontinue their GS-9131 or PTM but remain on their failing ARV regimen until the site is notified of the subject's eligibility to proceed to Part 2.
- d. [REDACTED]
- e. In Part 1 Randomized Cohort 2, Treatment Arms A-C will be assigned up to three dose levels of GS-9131, up to 180 mg. The GS-9131 dose for Treatment Arm A-C will be determined following review of the Sentinel Cohort 2. Doses of GS-9131 for subjects in the randomized cohorts A-C will correspond to the respective dose selected in Part 2. All subjects will continue a regimen of GS-9131+BIC+TAF at the assigned GS-9131 until determination of the optimal GS-9131 dose following Part 1 data review of the randomized cohort.

CCI

[REDACTED]

CCI

[REDACTED]

[REDACTED]

CCI [Redacted]

[Redacted]

[Redacted]

[Redacted]

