Safety data from Study GS-US-442-4148 demonstrated multiple daily doses of GS-9131 60 mg were well tolerated in HIV-infected subjects. Similarly, safety data from Study GS-US-180-4149 demonstrated multiple daily doses of GS-9131 60 mg, administered alone or in combination with DRV/COBI or TAF for up to 14 days, were well tolerated in healthy subjects. As no clinical safety data are currently available for GS-9131 180 mg, safety for these doses in female subjects are supported by safety margins in female animals in nonclinical toxicology studies. Safety margins relative to female animals in the nonclinical toxicology studies have been calculated for both GS-9131 and GS-9148 ([Table 1](#)). Safety, tolerability and PK of GS-9131 will be characterized in this study.

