5. INVESTIGATIONAL MEDICINAL PRODUCTS

5.1. Randomization, Blinding and Treatment Codes

It is the responsibility of the investigator to ensure that the subject is eligible for the study prior to enrollment. Subjects will be assigned a screening number at the time of consent.

Subjects who meet criteria will first be enrolled in the Sentinel Cohorts. The Sentinel Cohort 1 is an open-label cohort that will enroll 10 HIV-1 positive subjects to receive GS-9131 60 mg plus their current failing regimen for 10 days. The Sentinel Cohort 2 is an open-label cohort that will enroll up to 10 HIV-1 positive subjects to receive GS-9131 180 mg plus their current failing regimen for 14 days. Randomization and dosing of the Randomized Cohort of Part 1 will begin after the Day 15 safety, efficacy, and available PK data from the Sentinel Cohort 2 are reviewed.

Once eligibility has been confirmed for the Randomized Cohort and prior to or during the Part 1 Day 1 visit, the Investigator or designee will randomize the subject using the Interactive Web Response System (IWRS). Once a subject number has been assigned to a subject, it will not be reassigned to any other subject. The subject number assignment and randomization may be performed up to 3 days prior to the in-clinic Part 1 Day 1 visit provided that all screening procedures have been completed and subject eligibility has been confirmed. The Investigator must have results from genotype testing and confirmed eligibility before proceeding with subject randomization.

The IWRS will assign study drug bottle numbers of blinded GS-9131 or PTM at each study visit for each subject. At the beginning of Part 2, IWRS will assign GS-9131 + BIC + TAF.

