- b Results from the screening genotype report and confirmed eligibility must be obtained before proceeding with Day 1 Visit. Local genotype at the Screening Visit is acceptable for enrollment upon review by the Sponsor. A single 14 day extension to the screening window may be granted with permission from the Medical Monitor if the genotype results are delayed.
- c Randomization and dosing into the Randomized Cohort of Part 1 will begin after the Day 10 safety, efficacy and available PK data from the 10 subjects in the Sentinel Cohort are reviewed.

- d Before proceeding into Part 2, subjects who have completed Day 10 of Part 1 (from either the Sentinel or Randomized Cohorts) will discontinue GS-9131 or PTM but remain on their failing regimen until the site is notified of the subject's eligibility to proceed to Part 2. This period shall be no longer than 14 days while awaiting Day 10 HIV-1 RNA results and the authorization to proceed from Gilead. Once notified of their eligibility into Part 2 of the study, the subject will discontinue their failing regimen before initiating any Part 2 Day 1 study procedures. In the event the plasma HIV-1 RNA test results performed by the central laboratory are delayed beyond 14 days, a subject may still proceed to Part 2 of the study if the test results from the local laboratory show a reduction in plasma HIV-1 RNA $> 0.5 \log_{10}$ compared to pre-GS-9131 baseline after 10 days of GS-9131 functional monotherapy in Part 1 of the study.
- e All study visits are to be scheduled relative to the Part 2 Day 1 visit date. Visit windows are ± 4 days of the protocol specified date through Week 8, ± 4 days of the protocol specified date through Week 24. **CCI**
- f [REDACTED]
- g [REDACTED]
- h ESDD visit to occur within 72 hours of last dose of study drug. Subjects will be asked to continue attending the scheduled study visits through the Week 24 visit even as the subject discontinues study drug.
- i Any AE or test showing abnormal results that is believed to have a possible or probable causal relationship with the study drug will be repeated weekly (or as often as deemed prudent by the Investigator) until the abnormality is resolved, returns to baseline (Day 1) value, or is otherwise explained.

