HBV blood panel	X							X	X		
Plasma HIV-1 RNA	X	X	X	X	X	X	X	X	X	X	X
CD4+ Cell Count	X	X	X	X	X	X	X	X	X	X	X
HIV-1 Genotype/ Phenotype ^j											X
Timed PK Sample ^a				X		X	X				
Single Anytime PK Sample ^o			X		X			X			
Intensive PK Sampling ^p				X ^f	X ^f						
Collect Subject Dosing Diary to Subjects				X	X	X	X	X	X	X	X
Study Drug Dispensation ^u	X	X	X	X	X	X	X	X	X	X	
Drug Accountability	X	X	X	X	X	X	X	X	X	X	X

- a Evaluations to be completed within 30 days prior to Part 1 Day 1 visit. A single 14 day extension to the screening window may be granted with permission from the Medical Monitor
- b Results from the screening genotype report and confirmed eligibility must be obtained before proceeding with Day 1 Visit. Local genotype at the Screening Visit is acceptable for enrollment upon review by the Sponsor. A single 14 day extension to the screening window may be granted with permission from the Medical Monitor if the genotype results are delayed.
- c Randomization and dosing into the Randomized Cohort of Part 1 will begin after the Day 15 safety, efficacy and available PK data from the 10 subjects in the Sentinel Cohort 2 are reviewed.
- d Before proceeding into Part 2, subjects who have completed Day 14 of Part 1 (from either the Sentinel or Randomized Cohorts) will discontinue GS-9131 or PTM but remain on their failing regimen until the site is notified of the subject's eligibility to proceed to Part 2. This period shall be no longer than 9 days while awaiting HIV-1 RNA results and the authorization to proceed from Gilead. Once notified of their eligibility into Part 2 of the study, the subject will discontinue their failing regimen before initiating any Part 2 Day 1 study procedures. In the event the plasma HIV-1 RNA test results performed by the central laboratory are delayed, beyond 9 days, a subject may still proceed to Part 2 of the study if the test results from the local laboratory show a reduction in plasma HIV-1 RNA > 0.5 log₁₀ compared to pre-GS-9131 baseline during the 14 days of GS-9131 functional monotherapy in Part 1 of the study.
- e All study visits are to be scheduled relative to the Part 2 Day 1 visit date. Visit windows are ± 4 days of the protocol specified date through Week 24, CCI
- f [REDACTED]
- g [REDACTED]
- h ESDD visit to occur within 72 hours of last dose of study drug. Subjects will be asked to continue attending the scheduled study visits through the Week 24 visit even as the subject discontinues study drug.

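### Notes under the Cohort 1 schema and procedures table still give the Randomized Cohort a start gate, last dosing day and waiting period that differ from the body text and Appendix 3

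*Protocol*

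**What the plan says.** Figure 2 (protocol Section 3.4) and protocol Appendix 2 are both titled for Cohort 1, yet their notes set rules for the Randomized Cohort.

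- **Start.** Figure 2 note a: randomization and dosing "will begin after the Day 10 safety and efficacy data from the 10 subjects in the Sentinel Cohort are reviewed". Appendix 2 footnote c: "will begin after the Day 10 safety, efficacy and available PK data from the 10 subjects in the Sentinel Cohort are reviewed".
- **End of Part 1 dosing.** Figure 2 note c, on stopping GS-9131 or placebo: "Subjects who complete Day 10 of Part 1 (from either the Sentinel Cohort or Treatment Arm D of the Randomized Cohort) will discontinue". Appendix 2 footnote d is wider: "subjects who have completed Day 10 of Part 1 (from either the Sentinel or Randomized Cohorts) will discontinue GS-9131 or PTM". Footnote t puts all Part 1 study medication on Days 1-10.
- **Wait before Part 2.** Appendix 2 footnote d: "This period shall be no longer than 14 days while awaiting Day 10 HIV-1 RNA results".

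SAP Appendix 1 carries the same footnotes. Its Part 1 column header includes the word Randomized, its randomization row is marked on Day 1, and in-clinic dosing stops at Day 10.

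Other parts of the protocol differ. Section 5.1 says the Randomized Cohort "will begin after the Day 15 safety, efficacy, and available PK data from the Sentinel Cohort 2 are reviewed", and Section 6.3.1 and Appendix 3 footnote c agree. Section 3.3 gives 14 days of dosing. Section 5.3 and Appendix 3 footnote t give directly observed dosing on Days 1-14. Figure 3 note c ends dosing at Day 14. On the wait, Appendix 3 footnote d says "This period shall be no longer than 9 days while awaiting HIV-1 RNA results and the authorization to proceed from Gilead". Section 6.3.2 splits the limit by cohort: 14 days for Sentinel Cohort 1, 9 days for Sentinel Cohort 2 and the Randomized Cohort.

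**The concern.** These are working instructions in a schema and a visit table, which site staff follow day to day. Protocol Sections 6, 6.2.1 and 6.3.1 refer to Appendix 2 and Appendix 3 together without saying which cohort uses which. The only rule for resolving discrepancies that I found, in Section 7.6, concerns toxicity criteria.

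The primary endpoint is the proportion with a fall in HIV-1 RNA of more than 0.5 log10 at Day 15 in the Randomized Cohort (Section 8.1.2). It is meant to be read the day after 14 days of dosing. Section 1.7 gives suboptimal dose and duration as possible reasons for the low response in Sentinel Cohort 1, and that is its argument for the longer course. A randomized subject managed on the 10-day table would not contribute the measurement that the primary analysis assumes.

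**Working it through.** **The two sets of rules side by side**

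| Rule for the Randomized Cohort | Under Cohort 1 headings | Elsewhere in the protocol |
|---|---|---|
| Data reviewed before start | Day 10 data, 10 Sentinel subjects (Figure 2 note a; Appendix 2 footnote c) | Day 15 data, Sentinel Cohort 2 (Sections 5.1 and 6.3.1; Appendix 3 footnote c; Figure 3 note a also says Day 15) |
| Last day of GS-9131 or placebo | Day 10 (Figure 2 note c for Arm D; Appendix 2 footnote d for the Randomized Cohorts generally; footnote t for all Part 1 medication) | Day 14 (Sections 3.3 and 5.3; Figure 3 note c; Appendix 3 footnotes d and t) |
| Longest wait on the failing regimen alone | 14 days (Appendix 2 footnote d) | 9 days (Sections 3.3 and 6.3.2; Appendix 3 footnote d) |

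The SAP has the same split. Its Appendix 1 follows the middle column and its Appendix 2 the right-hand one.

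**Sizes**

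- Dosing days: 14 - 10 = 4 fewer, and 4/14 = 29% of the course.
- Last dose to a Day 15 sample: 15 - 10 = 5 days on the first set, 15 - 14 = 1 day on the second.
- Longest wait: 14 - 9 = 5 days' difference.

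**Effect on the primary endpoint**

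For the 10-day cohort the synopsis schedules the last Part 1 HIV-1 RNA sample on Day 11. For the Randomized Cohort it schedules Days 14 and 15. A randomized subject run on the 10-day schedule would therefore either have no Day 15 sample planned, or have one drawn 5 days after dosing stopped. Under Section 8.5.1 a missing Day 15 value counts as non-response. I had only the footnotes of protocol Appendix 2, not its grid. The Day 11 end point rests on the synopsis and on the SAP copy, whose Part 1 columns stop at Day 11.

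**The plan's own figure**

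The one design figure for this cohort is 85% power (Section 8.9). Exact enumeration for 12 against 12, 70% against 8.3%, Fisher's exact test at two-sided 0.05, gives 85.9% for a single comparison. That agrees with the stated figure, and nothing here depends on it: reconciling the text leaves it unchanged.

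**The case against.** The strongest reply is that the headings already settle the matter. Figure 2 and Appendix 2 are titled for Cohort 1, and Appendix 3 is titled for Sentinel Cohort 2 and the Randomized Cohort. The body text is consistent on 14 days and on Sentinel Cohort 2 as the gate, and Section 6.3.2 assigns the two waiting limits by cohort. On that view the notes are wording left in place when the second Sentinel Cohort was added. Much of this stands: it makes a mistake by a site less likely. It does not remove the contradiction, because the notes name the Randomized Cohort in terms and the SAP copy has a column header and a randomization row to match.

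A reader might also infer that randomized doses up to 180 mg could start on the 60 mg data alone, given the statement in Section 1.8.1: "As no clinical safety data are currently available for GS-9131 180 mg". The documents do not support that. The synopsis, Section 5.3 and Figure 3 note e make the doses for Arms A-C depend on review of Sentinel Cohort 2, and Section 3.3 says its data determine the doses. Section 1.9 ties evaluation of doses up to 180 mg to a median fall of more than 0.5 log in that cohort. Before that review there is no arm dose to assign.

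Nor do the documents support a reading that the Day 15 endpoint is lost for the whole cohort. That would require sites to use the Cohort 1 table against Sections 3.3 and 5.3 and Appendix 3.

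The conflict also has limits. Among randomized subjects, Figure 2 note c names only Arm D. The 14-day wait appears in Appendix 2, not in Figure 2. Figure 2 note b and Appendix 2 footnote s agree with their counterparts in Figure 3 and Appendix 3.

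**Conclusion.** The inconsistency is real and should be corrected, but it is modest. Three operating rules for the Randomized Cohort are each stated in two ways: the data reviewed before start (Day 10 Sentinel data or Day 15 Sentinel Cohort 2 data), the last dosing day (10 or 14) and the longest wait before Part 2 (14 or 9 days). It looks like carried-over wording.

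The practical risk is conditional on a site applying the Cohort 1 table to a randomized subject. For that subject the Day 15 sample would come 5 days after the last dose instead of 1, or would not be scheduled. How often this would happen cannot be estimated from the documents. That the first set refers to the 60 mg cohort is inferred from the Cohort 1 titles; the notes themselves give no dose.

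The reported analyses are not affected. SAP Sections 2.4 and 6 say the study was stopped on the Sentinel Cohort 2 criterion and that there are no efficacy data from the Randomized Cohort.

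**What to change.** Reconcile Figure 2 notes a and c, Appendix 2 footnotes c, d and t, and SAP Appendix 1 with protocol Sections 3.3, 5.1, 5.3, 6.3.1 and 6.3.2, Figure 3 and Appendix 3. The start gate, dosing days and waiting period for the Randomized Cohort should read the same wherever they appear. Which gate, duration and limit should stand is for the sponsor to decide; no view is taken here.

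The cost is a change to two figure notes, three footnotes and the SAP copy of the table. It adds no subjects, visits or procedures and does not alter the power calculation.

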4. SUBJECT POPULATION

4.1. Number of Subjects and Subject Selection

Up to 68 subjects who meet eligibility criteria will be enrolled.

Replacement subjects may be enrolled for subjects who do not complete all procedures in the GS-9131 14-day functional monotherapy treatment for reasons other than discontinuation due to treatment related AEs.

4.2. Inclusion Criteria

Subjects must meet **all** of the following inclusion criteria to be eligible for participation in this study.

- 1) The ability to understand and sign a written informed consent form, which must be obtained prior to initiation of study procedures
- 2) Non-pregnant/non-lactating females, ≥ 18 years of age at Screening
- 3) Plasma HIV-1 RNA ≥ 500 copies/mL at Screening Visit
- 4) Currently taking a failing ARV regimen that contains 2 NRTIs and an NNRTI
- 5) No prior or current ARV regimens containing integrase inhibitor (INSTI) or protease inhibitor (PI)
- 6) Screening genotype must show at least the following resistance mutation profile (a local genotype (within 3 months of the Screening visit) is acceptable for enrollment upon review by the Sponsor):
 - a) K65R or at least 3 TAMS (defined as: M41L, D67N, K70R, L210W, T215F/Y or K219Q/E/N/R) or Q151M
 - b) and at least one primary resistance mutation to an NNRTI (defined as L100I, K101E/P, K103N/R/S, V106M/A, V108I, E138A/G/K/Q/R, V179L, Y181C/I/V, Y188C/H/L, G190A/E/Q/S, H221Y, P225H, F227C or M230L/I)
- 7) Adequate renal function:

Estimated glomerular filtration rate ≥ 70 mL/min according to the Cockcroft-Gault formula for creatinine clearance {[Cockcroft 1976](#)}:

 - Female:
$$\frac{(140 - \text{age in years}) \times (\text{wt in kg}) \times 0.85}{72 \times (\text{serum creatinine in mg/dL})} = \text{CLcr (mL/min)}$$
$$\frac{(140 - \text{age in years}) \times (\text{wt in kg})}{72 \times (\text{serum creatinine in } \mu\text{mol/L}) \times 0.6786} = \text{CLcr (mL/sec)}$$

- 8) Normal ECG (or if abnormal, determined by the Investigator to be not clinically significant)
- 9) CD4 > 100 cells/ μ L
- 10) Hepatic transaminases (AST and ALT) $\leq 2 \times$ upper limit of normal (ULN)
- 11) Total bilirubin ≤ 1.5 mg/dL (≤ 26 μ mol/L), or normal direct bilirubin
- 12) Adequate hematologic function (absolute neutrophil count $\geq 750/\text{mm}^3$ (≥ 0.75 GI/L); platelets $\geq 50,000/\text{mm}^3$ (≥ 50 GI/L); hemoglobin ≥ 10 g/dL (≥ 100 g/L))
- 13) Serum amylase $\leq 2 \times$ ULN (subjects with serum amylase $> 2 \times$ ULN will remain eligible if serum lipase is $\leq 2 \times$ ULN)
- 14) A negative serum pregnancy test is required for female subjects of childbearing potential (as defined in [Appendix 7](#)). Female subjects of childbearing potential must agree to utilize protocol-recommended highly effective contraceptive methods or be non-heterosexually active or practice sexual abstinence (as defined in [Appendix 7](#))

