6.8.1. Blood Samples

- **Blood samples will be collected for the following laboratory analyses** (Refer to Appendix 2, and Appendix 3):
 - Serum pregnancy test (females of childbearing potential only). If the test is positive, the subject will not be enrolled (**Screening and Day 1 only**). Positive urine pregnancy tests will be confirmed with a serum test.
 - Follicle-stimulating hormone (FSH) (females who have ceased menstruating for greater than or equal to 12 months but do not have documentation of ovarian hormonal failure) Female subject post-menopausal for less than two year, if FSH < 40 mIU/ mL a serum pregnancy test will be required (**Screening only**)
 - Chemistry profile: alkaline phosphatase, AST, ALT, total bilirubin, direct and indirect bilirubin, total protein, albumin, CPK, bicarbonate, blood urea nitrogen (BUN), calcium, chloride, creatinine, glucose, phosphorus, magnesium, potassium, sodium, uric acid, amylase (reflex lipase testing is performed in subjects with total amylase > 1.5 × ULN)
 - Metabolic profile: Fasting (no food or drinks, except water, at least 8 hours prior to blood collection) glucose and lipid panel (total cholesterol, HDL, direct LDL, and triglycerides) collected at **Part 1 – Day 1, Part 2 – Day 1, Weeks 12** CCI [REDACTED].
 - If the subject has not fasted prior to the visit, the visit may proceed, but the subject must return within 72 hours in a fasted state to draw blood for the metabolic assessments

— eGFR according to the Cockcroft-Gault formula:

$$\text{Female: } \frac{(140 - \text{age in years}) \times (\text{wt in kg}) \times 0.85}{72 \times (\text{serum creatinine in mg/dL})} = \text{CLcr (mL/min)}$$

$$\frac{(140 - \text{age in years}) \times (\text{wt in kg})}{72 \times (\text{serum creatinine in } \mu\text{mol/L})} \times 0.85 = \text{CLcr (mL/sec)}$$

— Hematology profile: complete blood count (CBC) with differential and platelet count.

— CD4 cell count and percentage

— Plasma HIV-1 RNA

— HBV blood panel: Hepatitis B virus surface antigen serology (HBsAg), Hepatitis B virus surface antibody (HBsAb) and Hepatitis B virus core antibody (HBcAb)

The following tests will be conducted by the central laboratory if the following criteria are met:

- If positive HBsAg, reflex testing for plasma HBV DNA, Hepatitis B virus e-antigen (HBeAg) (if negative, reflex Hepatitis B virus e-Antibody [HBeAb]), and quantitative HBsAg.

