Blood Urea Nitrogen	1.25 to 2.50 × ULN	> 2.50 to 5.00 × ULN	> 5.00 to 10.00 × ULN	> 10.00 × ULN
Hyperuricemia	> ULN to 10.0 mg/dL > ULN to 597 μmol/L	> 10.0 to 12.0 mg/dL > 597 to 716 μmol/L	> 12.0 to 15.0 mg/dL > 716 to 895 μmol/L	> 15.0 mg/dL > 895 μmol/L
Hypouricemia Adult and Pediatric ≥ 1 year	1.5 mg/dL to < LLN 87 μmol/L to < LLN	1.0 to < 1.5 mg/dL 57 to < 87 μmol/L	0.5 to < 1.0 mg/dL 27 to < 57 μmol/L	< 0.5 mg/dL < 27 μmol/L
Infant < 1 Year	N/A	1.0 mg/dl to < LLN- 57 μmol to < LLN	0.5 to < 1.0 mg/dL 27 to < 57 μmol/L	< 0.5 mg/dL < 27 μmol/L
Creatinine**	> 1.50 to 2.00 mg/dL > 133 to 177 μmol/L	> 2.00 to 3.00 mg/dL > 177 to 265 μmol/L	> 3.00 to 6.00 mg/dL > 265 to 530 μmol/L	> 6.00 mg/dL > 530 μmol/L

CHEMISTRY				
	Grade 1	Grade 2	Grade 3	Grade 4
Bicarbonate Adult and Pediatric ≥ 4 Years	16.0 mEq/L to < LLN	11.0 to < 16.0 mEq/L	8.0 to < 11.0 mEq/L	< 8.0 mEq/L
	16.0 mmol/L to < LLN	11.0 to < 16.0 mmol/L	8.0 to < 11.0 mmol/L	< 8.0 mmol/L
Pediatric < 4 Years	NA	11.0 mEq/L to < LLN 11.0 mmol/L to < LLN	8.0 to < 11.0 mEq/L 8.0 to < 11.0 mmol/L	< 8.0 mEq/L < 8.0 mmol/L
Triglycerides (Fasting)	NA	500 to 750 mg/dL 5.64–8.47 mmol/L	> 750 to 1200 mg/dL > 8.47–13.55 mmol/L	> 1200 mg/dL > 13.55 mmol/L
LDL (Fasting) Adult	130 to 160 mg/dL 3.35 to 4.15 mmol/L	>160 to 190 mg/dL >4.15 to 4.92 mmol/L	> 190 mg/dL >4.92 mmol/L	NA
LDL (Fasting) Pediatric >2 to <18 years	110 to 130 mg/dL 2.84 to 3.37 mmol/L	>130 to 190 mg/dL >3.37 to 4.92 mmol/L	> 190 mg/dL >4.92 mmol/L	NA
Hypercholesterolemia (Fasting)	200 to 239 mg/dL 5.16 to 6.19 mmol/L	> 239 to 300 mg/dL > 6.19 to 7.77 mmol/L	> 300 mg/dL > 7.77 mmol/L	NA
	Pediatric < 18 Years 170 to 199 mg/dL 4.39 to 5.15 mmol/L	> 199 to 300 mg/dL > 5.15 to 7.77 mmol/L	> 300 mg/dL > 7.77 mmol/L	NA
Creatine Kinase	3.0 to < 6.0 × ULN	6.0 to < 10.0 × ULN	10.0 to < 20.0 × ULN	≥ 20.0 × ULN

* Calcium should be corrected for albumin if albumin is < 4.0 g/dL

** An overlap between the Grade 1 scale and the Lab's normal range for creatinine may result for Male subjects >70 yrs. Please follow the Gilead convention of grading any result within the LLN and ULN a 0.

ENZYMES				
	Grade 1	Grade 2	Grade 3	Grade 4
AST (SGOT)	1.25 to 2.50 × ULN	> 2.50 to 5.00 × ULN	> 5.00 to 10.00 × ULN	> 10.00 × ULN
ALT (SGPT)	1.25 to 2.50 × ULN	> 2.50 to 5.00 × ULN	> 5.00 to 10.00 × ULN	> 10.00 × ULN
GGT	1.25 to 2.50 × ULN	> 2.50 to 5.00 × ULN	> 5.00 to 10.00 × ULN	> 10.00 × ULN

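### The two µmol/L Cockcroft-Gault formulas for women differ from each other by a factor of 1.73, and neither equals the female mg/dL formula printed beside it

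*Protocol*

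**What the plan says.** Protocol 4.2, criterion 7, sets the limit: "Estimated glomerular filtration rate ≥ 70 mL/min according to the Cockcroft-Gault formula". Under the label Female it prints two formulas. The mg/dL version carries the sex factor: "wt in kg}) \times 0.85}{72 \times (\text{serum creatinine in mg/dL})} = \text{CLcr (mL/min". The µmol/L version is (140 − age) × weight divided by 72 × creatinine × 0.6786, ending "0.6786} = \text{CLcr (mL/sec", with no 0.85.

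Section 6.8.1 repeats the mg/dL formula unchanged. Its µmol/L version is (140 − age) × weight divided by 72 × creatinine, then multiplied by 0.85, ending "0.85 = \text{CLcr (mL/sec", with no 0.6786.

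Enrolment is restricted to women ("Non-pregnant/non-lactating females, ≥ 18 years of age at Screening"), so the sex factor applies to every subject. The SAP repeats the 70 mL/min limit in its key eligibility criteria and lists baseline eGFR in mL/min in Section 5.2. Its programming specification (SAP Appendix 3) defines BMI and body surface area but gives no eGFR formula. Neither document says whether sites or the laboratory calculate from mg/dL or from µmol/L.

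**The concern.** A formula inside a numeric entry criterion should give the same answer whatever unit the laboratory reports. Here the two µmol/L lines each lack a different factor, so the same woman can fall on either side of 70 mL/min depending on which printed line is used. The error is also hard to see afterwards. The eligibility listing in SAP 4.3 covers subjects who did not meet a criterion, so a woman passed by the 4.2 µmol/L line would simply be recorded as eligible. eGFR is also scheduled repeatedly in Part 1 and at every Part 2 visit, and a site working in µmol/L would have two incompatible definitions to choose from.

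**Working it through.** **Inputs**

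- Reference: the protocol's own female mg/dL formula, (140 − age) × weight × 0.85 / (72 × creatinine in mg/dL), in mL/min (4.2 and 6.8.1).
- Limit: 70 mL/min = 70/60 = 1.167 mL/sec.
- Creatinine conversion, from the grade limits in Protocol Appendix 5 (for example "> 6.00 mg/dL > 530 μmol/L"): 133/1.5 = 88.67, 177/2 = 88.5, 265/3 = 88.33, 530/6 = 88.33 µmol/L per mg/dL. I use 88.4 and carry the range 88.33 to 88.67.

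**Where the printed constant comes from**

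Converting mg/dL to µmol/L and minutes to seconds gives 60/88.4 = 0.6787, which matches the printed 0.6786. With the sex factor folded in, the constant would be 60/(88.4 × 0.85) = 0.7985, which does not match. So 0.6786 is a unit conversion only, and 0.85 is still needed.

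**The three formulas on one scale**

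Let K = (140 − age) × weight / (72 × creatinine in µmol/L). In mL/sec:

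| Formula | Multiple of K | Ratio to reference (range) |
|---|---|---|
| Female mg/dL formula, converted | 0.85 × 88.4/60 = 1.2523 | 1 |
| µmol/L line in 4.2 | 1/0.6786 = 1.4736 | 1.177 (1.173 to 1.178) |
| µmol/L line in 6.8.1 | 0.85 | 0.679 (0.677 to 0.679) |

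The two µmol/L lines differ by 1.4736/0.85 = 1.734, whatever conversion factor is used.

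**At the limit**

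- A reading of 70 on the 4.2 line corresponds to 70/1.1767 = 59.5 mL/min by the mg/dL formula (59.4 to 59.7).
- A value of 70 by the mg/dL formula reads 70 × 0.679 = 47.5 on the 6.8.1 line. To read 70 there, a woman would need about 103 mL/min.

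**Worked example: age 40, 55 kg, creatinine 88.4 µmol/L (1.0 mg/dL)**

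- mg/dL formula: 100 × 55 × 0.85 / 72 = 64.9 mL/min, not eligible.
- 4.2 µmol/L line: 5500 / (72 × 88.4 × 0.6786) = 1.273 mL/sec = 76.4 mL/min, eligible.
- 6.8.1 µmol/L line: 5500 / (72 × 88.4) × 0.85 = 0.735 mL/sec = 44.1 mL/min, not eligible.

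**With both factors present**

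(1/0.6786) × 0.85 = 1.2526, against 1.2523 for the reference: ratio 1.0002 (0.997 to 1.001 over the conversion range).

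**The case against.** *The equations may have been damaged when the PDF was read.* The gaps are complementary, so if one factor was lost from each line, the source could be consistent and correct. This cannot be ruled out from the extracted text. It would, however, need a different factor to be lost from each of two otherwise complete equations while both mg/dL equations survived. That is possible but unlikely, and it is why the fix starts with the source PDF.

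*The µmol/L line may never be used.* The limit is stated in mL/min, the unit of the mg/dL formula; the µmol/L line gives mL/sec and needs a further conversion that the protocol does not describe. This stands. A reader might infer that women near 60 mL/min were admitted, but the documents support only that they could be, if the 4.2 µmol/L line is applied as printed. The 59.5 is also not a true or measured clearance. It is the value from the protocol's own mg/dL formula.

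*Baseline against follow-up.* A reader might infer that 4.2 governs eligibility and 6.8.1 governs on-study eGFR, so that moving from one to the other mimics a fall of 1 − 44.1/76.4 = 42%. The documents make no such split. Section 6.2.1 sends screening samples to 6.8.1, and the Appendix 3 schedule includes eGFR at Screening.

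*Effect on results.* SAP 7.2 bases the laboratory analysis on conventional units, and SAP 5.2 lists eGFR in mL/min. That points to the mg/dL formula, so the planned summaries should not be distorted. eGFR is not an efficacy endpoint, Appendix 5 grades serum creatinine directly, and Protocol 6.5 and 6.5.1 name no eGFR value. SAP 2.4 and 6 report that the study stopped without efficacy data from the Randomized Cohort, so few subjects are affected. All of this limits the consequence but does not make the printed formulas agree.

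**Conclusion.** As printed, the µmol/L formulas in 4.2 and 6.8.1 cannot both be right for women, and neither agrees with the mg/dL formula beside it. The 4.2 line omits the sex factor and reads about 18% high; the 6.8.1 line omits the unit constant and reads about 32% low. The first could let through women between about 59.5 and 70 mL/min by the protocol's own mg/dL formula. The second could wrongly exclude women between 70 and about 103. Either error arises only where eligibility or a site eGFR was calculated from µmol/L with the line as printed, and the documents do not say whether that happened. The ratios rest on the mg/dL formula as reference and on a conversion of 88.33 to 88.67, which hardly moves them. The conclusion also assumes that the extracted equations match the source PDF.

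**What to change.** 1. Check both µmol/L equations against the source PDF.
2. If they stand as extracted, reconcile Sections 4.2 and 6.8.1 with the protocol's own mg/dL formula by printing the same line in both: (140 − age) × weight × 0.85 / (72 × creatinine in µmol/L × 0.6786) = mL/sec.
3. Beside the existing 70 mL/min limit, give its unit equivalent, 1.17 mL/sec. The limit itself does not change.
4. For any subject assessed with a µmol/L formula, recompute screening eGFR from stored creatinine, age and weight, and record any change in eligibility status as a deviation.

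The cost is a wording correction in two sections and a short recalculation from data already held. No new data collection is needed, and the planned analyses do not change.
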